1.3.2 Principles of the Aspiration Therapy

Diet education and behavior modification has had limited success in managing obesity. Even patients who are able to achieve short-term weight loss are often unable to maintain the changes in eating behavior necessary to maintain successful long-term weight management. One of the key principles of dietary weight loss is to decrease calorie intake by decreasing meal portion size. The AspireAssist provides obese persons with the ability to achieve successful portion control at the level of the proximal gastrointestinal tract, so that a portion of ingested food is removed from the stomach, preventing its delivery into the small intestine for absorption. In addition, Aspiration Therapy is a comprehensive system for weight loss, which involves careful medical monitoring to ensure clinical safety, in conjunction with behavioral therapy to change unhealthy eating and physical activity behaviors.

The AspireAssist will be used within a structured and regulated medical and behavioral education program. Subjects will aspirate a portion of gastric contents after consuming each of the three major meals daily. The rate of weight loss will be controlled by careful monitoring and by regulating the frequency of postprandial aspirations. The goal is for subjects to lose ~1.0% body weight per week until energy balance is achieved at a healthier BMI. Medical risk caused by overuse or "abuse" of the AspireAssist™ by study subjects is highly unlikely for the following reasons:

- 1. Most obese persons are trying to reach a healthier body weight and do not desire to be underweight; they do not suffer from anorexia nervosa.
- 2. Subjects who have evidence of psychological abnormalities that could increase the risk of non-adherence with the study protocol will be excluded from participation.
- 3. The study protocol requires frequent, careful and comprehensive medical monitoring to reduce the risk of complications.
- 4. The number of aspirations is monitored by a cycle counter within the Connector. When the cycle counter reaches a preset limit (i.e. approximately 6 weeks of aspiration sessions) aspiration through the A-Tube™ will not be mechanically possible. A new Connector, which can only be provided by the study site, will be required to allow continued aspiration. Therefore, subjects must return regularly to the study site for continued access to the A-Tube.
- 5. If a subject experiences rapid or excessive weight loss, the frequency of postprandial gastric aspirations will be decreased or Aspiration Therapy stopped completely until the subject responds to retraining.
- 6. The study protocol involves a behavioral and diet education program to change unhealthy lifestyle behaviors, which takes advantage of the reduced threshold for achieving weight management success provided by the AspireAssist.
- 7. The anticipated daily absorption of calories and rate of weight loss is safe. The weight loss goals of subjects in this study are equivalent to adherence

with a low-calorie diet (~1200 kcal to 1800 kcal/day) by combining a balanced deficit diet with aspiration therapy that decreases the absorption of calories from major meals by ~30%.

Subjects in the AT Group, on average, continued to lose weight after the 52-week period. At 64, 96, and 104 weeks respectively, mean %EWL was 56.6% \pm 10.9% (N=8) group, 56.9% \pm 12.2% (N=7), and 54.7% \pm 12.0% (N=7). At 52, 64, 96, and 104 weeks respectively, mean %weight loss was 18.6% \pm 2.3%, 21.2 \pm 3.1%, 21.0 \pm 3.5%, and 20.1 \pm 3.5% respectively, and mean absolute weight loss was 20.6 \pm 2.5 kg, 23.0 \pm 3.2 kg, 22.3 \pm 3.5 kg, and 21.3 \pm 3.4 kg respectively.

Average total Impact of Weight on Quality of Life score (IWQOL) improved by 34.4 % and 20.0 % after 52 weeks of therapy in the AT and control groups, respectively. Technical success of A-TubeTM implantation was 100% in the 11 AT subjects.

1.3.4 AspireAssist Components and Use

Please refer to the Investigator's Brochure for a complete overview of the device.

Briefly, the AspireAssist consists of five components: one (1) implantable component (the A-Tube), three (3) external components, and one (1) component used for installation and adjustment purposes, each of which is described below.

- The A-TubeTM is similar in design and implantation techniques (via endoscopic pull-through method) to a standard PEG tube. The external portion of the A-Tube is cut to a length (using the Skin-Port Installation Tool Kit) so that it is almost flush with the abdominal skin, and its length is adjusted, by a healthcare professional, as the subject loses weight.
- The Skin-Port[™] connects to the proximal end of the A-Tube and prevents the tube from migrating into the stomach. The Skin-Port contains a valve that is normally closed to prevent gastric leakage, and is opened, by engaging the Connector (see below), when the subject aspirates after a meal. The Skin-Port is installed by a healthcare professional (using the Skin-Port Installation Tool Kit) but operated by the subject (solely through engaging and disengaging the Connector).
- The Connector™ mates with the Skin-Port and allows coupling between the A-Tube and the Companion (see below). The Skin-Port valve opens when the subject connects the Connector to the Skin-Port and closes when the subject disconnects the Connector. The Connector contains a "counter" that tracks the number of times the Connector is attached to the Skin-Port. When the count reaches 115 aspiration cycles (about 5 6 weeks of therapy), the Connector locks up and the Skin-Port can no longer be accessed for aspiration. This provides an additional safety measure against long-term unsupervised use or overuse. The subject must return to the clinic to obtain a new Connector in order to continue aspiration therapy.
- The CompanionTM allows the subject to aspirate his/ her gastric contents by alternately draining stomach contents and infusing (potable) water into

the stomach when the apparatus is fully connected (see **Figure 1.2.1**). The Companion is an entirely passive device and is reusable.

• The Skin-Port™ Installation Tool Kit facilitates (i) cutting of the A-Tube to length and (ii) removal and installation of the Skin-Port, both procedures done by the healthcare professional.

1.3.4.1 Principles of Operation

The AspireAssist is intended to assist in weight reduction of obese subjects. The therapy begins after the stoma track is healed 10 days after A-Tube placement. **Figure 1.2.1** illustrates typical use of AspireAssist.

[figure not shown]

Figure 1.2.1. Patient using the AspireAssist

Per the instructions for use, subjects are instructed to aspirate 20-30 minutes after a meal. In the Proof of Principle Trial, 20-30 minutes was found to be the optimal time period for aspiration: the particle size of ingested food in the stomach was sufficiently small to allow aspiration without clogging the tube and yet minimal amounts of food had passed to the intestines.

Prior to beginning aspiration, the subject must connect the apparatus as follows:

Fill the reservoir with potable water

- Attach the Connector tube and Drain Tube to the T-Fitting, then insert into the Companion with the arrow pointing down. Place the Lanyard of the Companion around his/her neck
- Attach the Connector to the Connector Tube
- Attach the Reservoir to the Companion

To begin aspiration, the subject, while standing in the upright position, attaches the Connector to the Skin-Port, and the Drain Clamp on the Companion is opened to drain. The Connector when attached to the Skin-Port opens the valve and initiates the aspiration process. After the initial stomach contents are evacuated, water is infused into the stomach by closing the Drain Clamp and squeezing the Reservoir. Infusion aides to further mobilize food trapped in gastric folds and aspiration is repeated to remove the water and food from the stomach. The infusion and aspiration of water is repeated until there are no food particles observed in the evacuated fluid. Based upon energy balance studies conducted in two subjects, this process will remove approximately 30% of the ingested calories from that meal. The final step in the process is to disconnect the Connector from the Skin-Port and rinse the system out for later use.

The entire aspiration process typically takes between 5 and 10 minutes.

1.3.4.2 Training

Prior to study initiation, each endoscopist placing the A-Tube will undergo training with an experienced endoscopist and qualified Aspire personnel. In addition, investigators and designees will be fully trained on the AspireAssist Aspiration Therapy System Instructions for Use, as well as procedures for training research subjects on AspireAssist use and Aspiration Therapy. Documentation of training will be kept at each study site.

Training of study subjects will be performed by the research team at each study site.

All principal investigators, co-investigators, and designees will be trained on this clinical investigation plan prior to involvement in this clinical trial. Documentation of training will be kept current at each study site.

2.0 Study Objective

The objective of this study is to demonstrate the safety and efficacy of the AspireAssist™ Aspiration Therapy System as a weight loss therapy for obese adults.

2.1 Primary Efficacy Endpoints (52-week)

The first effectiveness primary endpoint is the mean percent excess weight loss (%EWL) at 52-weeks. The hypothesis for the first primary effectiveness endpoint is that the difference in the mean percent excess weight loss (%EWL) at 52-weeks for the Aspiration Therapy (AT) group and Control group is at least 10%. %EWL is defined as absolute weight loss divided by baseline excess weight and multiplied by 100. Excess weight will be determined from ideal body weights based on a BMI=25 kg/m².

The second effectiveness primary endpoint is that at least 50% of the AT group at 52-weeks realizes a %EWL \geq 25%.

Both primary endpoints must be met for the study to be considered a success.

2.2 Secondary Efficacy Endpoints (52-week)

- i) Mean percent absolute weight loss in the AT group compared to the Control group
- ii) Proportion of subjects who achieve ≥10% absolute weight loss in the AT group compared to the Control group

The percent change in the AT Group compared with the percent change in the Control Group will be assessed for the following variables:

- iii) Serum triglyceride, HDL-cholesterol and LDL-cholesterol concentration
- iv) Systolic and diastolic blood pressures
- v) "Impact of Weight on Quality of Life" (IWQOL) questionnaire
- vi) Hemoglobin A1C (for subjects with T2 diabetes at screening only)
- vii) mean percent change in medications

In the AT group only:

viii) Procedural success defined as successful endoscopic placement of the A-TubeTM in all subjects undergoing endoscopy

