5.3 Control Group

Subjects randomized to the Control Group will participate in 14 Medical & Study visits and a 10-session diet and behavioral education weight loss

program called "Lifestyle Therapy" (see **Appendix C**), which will be delivered to subjects over 52 weeks. These Lifestyle Therapy sessions may be given individually during the same visit as the Medical & Study visits or in a group with other subjects who are assigned to the Control Group.

Each individual Lifestyle Therapy session will last 20-30 minutes and group sessions, about 60 minutes; the sessions will be given at week 0, 2, 6, 10, 14, 20, 28, 36, 44, and 52.

Topics include includes nutritional, physical activity, and behavioral education topics. Subjects are instructed to follow a structured eating plan, which involves eating three meals a day, eating slowly and chewing food well, drinking plenty of fluids with each meal, and limiting snacking between meals. Physical activity topics include the health benefits of physical activity and strategies for increasing lifestyle activity. The behavioral program emphasizes strategies of self-monitoring and goal-setting, and includes problem-solving, dealing with high-risk situations / cues for unhealthy eating, and stress management.

All subjects will be asked to take a multivitamin and mineral supplement daily during the lifestyle intervention program.

The Medical & Study visits occur at weeks 0, 2, 6, 10, 14, 20, 24, 28, 32, 36, 40, 44, 48, and 52, as outlined in the study assessment schedule in **Table 3**.

All Medical & Study visits will include the following assessment and procedures:

- Body weight
- Blood pressure and temperature
- Presence of normal menses in women
- Adverse Events
- Concomitant medications
- Adherence with taking study-related medications (i.e. multivitamin supplement)
- Lifestyle Therapy (only at weeks 0, 2, 6, 10, 14, 20, 28, 36, 44, and 52)

Additional procedures and assessments are performed at visits as shown in **Table 3**:

- Blood tests
- Urine (dipstick) protein test

- Physical Examination
- EKG
- Eating Disorder Examination (EDE)
- DEXA
- Questionnaires (IWQOL, QEWP-R)

If a subject develops 2+proteinuria (100mg/dL) as measured by two successive dipstick analyses, random urine shall be collected to measure protein and creatinine to calculate protein to creatinine ratio.

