5.4.4 Vitamins and Minerals

All subjects will take a multivitamin and mineral supplement daily. Additional iron supplementation (ferrous sulfate 325 mg/day taken with orange juice) should be considered in menstruating women who have a blood hemoglobin value <12 g/dL. The multivitamin and mineral supplement should be taken at night before going to sleep or least 2 hours before subjects aspirate gastric contents.

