5.5.3 Serum Potassium

A decrease in serum potassium concentration can occur with repeated aspiration of gastric contents, because of the loss of gastric acid and compensatory potassium excretion by the kidney. Therefore, serum potassium concentrations will be closely monitored in study subjects. The following protocol shall be followed to reduce the risk of hypokalemia:

a. Ensure appropriate initial serum potassium concentrations. Serum K concentration must be ≥3.8 mEq/L before starting Aspiration Therapy. If a potential subject has a serum K concentration that is <3.8, an attempt should be made to identify causal factors (e.g. history of diuretic therapy) so that any precipitating cause can be addressed to reduce the risk of future hypokalemia. Treatment with oral potassium supplements can be given until serum K concentration is ≥3.8 mEq/L, if Aspiration Therapy is desired in this subject.

b. Monitoring serum potassium concentration. Serum K concentration must be monitored regularly throughout the use of Aspiration Therapy (See Schedule of Assessments, Tables 1-3). No additional medical intervention is necessary if serum K concentrations remain ≥3.8 mEq/L and <5.6 mEq/L.

c. Managing a decline in serum potassium to <3.8 mEq/L.

- i. Serum potassium concentration decreases to 3.3-3.7 mEq/L. A decline in serum K to 3.3-3.7 mEq/L requires additional monitoring and intervention. First, a medical history should be obtained to identify other possible causes for hypokalemia. If a cause for the decline in serum K is identified (e.g. non-adherence with therapy, or taking a new medication that causes hypokalemia), this problem should be addressed. Potassium supplementation should be implemented or adjusted and serum K monitored frequently (one or more times/week) until serum K concentration returns to values ≥3.8 mEq/L. Aspiration Therapy can continue while additional potassium therapy is being given.

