8.2 Statistical Methods

Tabulation of summary statistics, graphical presentations, and statistical analyses will be performed using SAS® software. Where not otherwise specified, the last pre-treatment (i.e. for treatment group, this is prior to the initiation of therapy) observation will be used as baseline for calculating post-treatment changes from baseline. The primary presentations and analyses will be based on data pooled across study centers. Relevant summaries for individual centers, or combinations of centers, may be presented for primary data. All testing and confidence intervals will use a significance level of 5%.

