8.5.4 Secondary Efficacy Endpoints

The percent change from baseline will be calculated for all major time points and the results will be summarized for each group. Within treatment group differences will be tested using a Students T-test for paired samples on the percentage change from baseline at each study visit. Difference between treatment groups will be tested by using the two-sample t-test or Wilcoxon Test whenever appropriate.

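### The medication endpoint is a per-subject percent change, which is undefined for anyone on no medication at baseline and lopsided on small counts

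*Protocol*

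**What the plan says.** Section 2.2 lists "mean percent change in medications" among the 52-week secondary endpoints, under the lead-in "The percent change in the AT Group compared with the percent change in the Control Group will be assessed for the following variables". The Synopsis repeats it as item viii. Neither place says what is counted (items, doses or classes) or which medications qualify.

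Section 8.5.4 gives the calculation and the tests: "The percent change from baseline will be calculated for all major time points", and "Within treatment group differences will be tested using a Students T-test for paired samples on the percentage change from baseline at each study visit". Between groups it allows a two-sample t-test or a Wilcoxon test. Section 8.2 defines the divisor: "the last pre-treatment (i.e. for treatment group, this is prior to the initiation of therapy) observation will be used as baseline".

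The protocol also prescribes items of its own. For Control, section 5.3 says "All subjects will be asked to take a multivitamin and mineral supplement daily during the lifestyle intervention program". For AT, section 5.4.4 says "All subjects will take a multivitamin and mineral supplement daily" and asks that iron be considered in menstruating women with low hemoglobin. Section 5.5.3, also for AT, says that when serum potassium falls "Potassium supplementation should be implemented or adjusted". Sections 5.3 and 5.5.1 describe the multivitamin as a study-related medication, but list adherence to it as a separate visit item from concomitant medications.

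Section 8.1.3 says that secondary endpoint data will only be tabulated and will not count as proof of efficacy.

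**The concern.** A percent change divides by the baseline value. No inclusion criterion in 4.1 requires a subject to be on medication. Section 4.2 removes several groups of drug users: insulin or sulfonylurea, recent weight-loss drugs, and drugs that cause weight gain. Subjects with a baseline of zero are therefore foreseeable. Section 2.2 limits HbA1c to subjects with type 2 diabetes but gives this endpoint no subset and no rule for a zero baseline.

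Three things are at stake. The endpoint would describe only subjects already on medication, and would miss drug starts among the rest. Its mean could be driven by subjects with one or two drugs. And because the word medications is left open, items that the study itself prescribes could enter the count, some of them described only for AT.

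The measure has a use. Sections 5.3, 5.4.5 and 5.8 expect diabetes drugs to change during the study, so a workable summary of drug use would help in reading the HbA1c, blood pressure and lipid results.

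**Working it through.** The protocol gives no sample size, power or expected value for this endpoint, so there is no stated figure to reproduce. The steps below treat medications as a count, which is an assumption. A zero baseline is undefined in any unit.

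1. **Formula.** Percent change = 100 × (week 52 − baseline) / baseline, one value per subject, as the test in 8.5.4 requires.

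2. **Zero baseline.** With baseline 0 the divisor is 0 and no value exists, whether the subject starts no drugs or several.

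3. **How many subjects.** The protocol gives no baseline distribution. Assume Poisson counts with mean m, so the share at zero is exp(−m). Planned sizes are 117 AT and 58 Control (8.1.1).

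| m | share at zero | AT (of 117) | Control (of 58) | total (of 175) |
|---|---|---|---|---|
| 1 | 0.368 | 43.0 | 21.3 | about 64 |
| 2 | 0.135 | 15.8 | 7.8 | about 24 |
| 3 | 0.050 | 5.8 | 2.9 | about 9 |

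4. **Lopsided scale.** From 1 to 2 is (2 − 1)/1 = +100%. From 5 to 4 is (4 − 5)/5 = −20%. Take one subject of the first kind and five of the second. The mean is (100 − 5 × 20)/6 = 0%, although total drugs fell from 1 + 25 = 26 to 2 + 20 = 22.

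5. **One supplement counted after baseline.** A subject who stops one drug and starts one supplement scores 0% instead of −100%, −50% or −33% (baseline 1, 2 or 3).

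6. **Effect on the comparison between arms.** This is an illustrative simulation among subjects with baseline of at least 1. Each drug is stopped with probability 0.3 in AT and 0.1 in Control, and there are no other starts. The stopping rates are assumptions.

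| m | no supplement counted: AT, Control, difference | one counted in every subject of both arms: AT, Control, difference | one counted in every AT subject only: difference |
|---|---|---|---|
| 1 | −30.0, −10.1, −19.9 | +46.8, +66.7, −19.9 | +56.8 |
| 2 | −30.0, −10.0, −20.0 | +27.7, +47.7, −20.0 | +37.7 |
| 3 | −30.0, −10.0, −20.0 | +13.2, +33.2, −20.0 | +23.2 |

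An item common to both arms moves both means above zero but leaves the difference unchanged. An item counted in AT only can reverse it.

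7. **How common an AT-only item would have to be.** Giving every AT subject one item shifts the AT mean by 46.8 + 30.0 = 76.8, 27.7 + 30.0 = 57.7 or 13.2 + 30.0 = 43.2 points. If the shift is proportional to the share affected, the difference is erased at 19.9/76.8 = 26%, 20.0/57.7 = 35% or 20.0/43.2 = 46% of AT subjects. The protocol gives no expected rate of potassium or iron use at week 52 to set against these shares.

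**The case against.** A reader might infer that the endpoint counts the supplements and so cannot show a reduced need for drugs. The documents do not support that.

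- Section 2.2 is silent on what counts, and the separate visit items in 5.3 and 5.5.1 would let supplements be kept apart. The accurate statement is that the wording does not exclude them.
- The multivitamin is given in both arms and largely cancels between them (step 6). When it starts relative to baseline is not stated. In AT the baseline may fall after A-Tube placement, so the supplement may already be in the divisor.
- Potassium and iron are conditional, and nothing says they would still be in use at week 52. The reversal in step 6 gives an item to every AT subject, which the protocol does not describe.

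Other points also carry weight. The Wilcoxon option in 8.5.4 blunts the lopsided scale in the between-group test, though not in the reported mean. Concomitant medications are recorded at each visit and tabulated by group (8.3), so the raw information is not lost. A separate statistical analysis plan, not seen here, may define which drugs count. No labeling claim rests on this endpoint (8.1.3).

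None of this answers the zero baseline. A rank test also needs a value to rank. Taking the percent change in each arm's mean count would avoid the problem, but that is not the per-subject quantity that 8.5.4 tests. Nor is this only a detail left for later: the protocol itself fixes the metric, and a later plan could repair it only by departing from it.

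**Conclusion.** The point holds in a limited form. As fixed in 2.2 and 8.5.4, the endpoint has no value for subjects on no medication at baseline, omits any drugs they start, and has a mean that is lopsided on small counts. The first and last of these follow from arithmetic alone. The number of subjects lost is not known: about 9 to 64 of 175 under Poisson baseline means of 3 down to 1, which are assumptions.

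The supplement issue is secondary and conditional. Only AT-only items could materially bias the comparison between arms, and only if they are counted and common enough at week 52. Because secondary endpoints are descriptive, this is a low-priority improvement and does not threaten the trial's conclusions.

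**What to change.** In Synopsis item viii and section 2.2 item vii, replace the endpoint with:

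- the change from baseline to week 52 in the number of concomitant antihypertensive, lipid-lowering and glucose-lowering drugs, shown by class and compared between arms; and
- for each class, the proportion of subjects whose treatment was decreased or stopped, unchanged, or increased or started.

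State that subjects with none at baseline are included, and that study-prescribed supplements (multivitamin and mineral, iron, potassium) and peri-procedural antibiotics and analgesics are excluded. In 8.5.4, say that the percent-change calculation does not apply to this endpoint.

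The cost is the extra coding by class of medications already recorded at each visit. No new visits, data or subjects are needed. Drugs outside the three classes would no longer enter the endpoint, but can still be tabulated.
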